2. STUDY DESIGN

The study is designed as a prospective, randomized (two-cohort) double-blinded clinical evaluation and will be conducted at multiple centers throughout the United States. Approximately 500 patients will be included and followed for a period of 2 years. Clinical Assessments will be performed at baseline, 6 weeks, 6 months, 1 and 2 years after surgery.

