5. METHODS / PROCEDURES

Patients indicated for TKA and who meet all study eligibility criteria will be asked to participate in the study. Eligible patients will receive a primary unilateral PCL-retaining or – sacrificing TKA using the Stryker Triathlon Total Knee System *with* or *without* the use of the VERASENSE™ Knee System. Patients will be enrolled in a consecutive series consisting of two cohorts (Groups A and B). Both groups are described below:

Group A – Control (Surgeon-Guided) will consist of **250** consecutive patients who will undergo primary unilateral PCL-retaining or – sacrificing TKA using the Stryker Triathlon Total Knee System *without* the use of VERASENSE to guide rotational alignment and balance. **Prior to closing the arthrotomy, VERASENSE will be utilized in a surgeon-blinded fashion to record rotational alignment and intercompartmental pressures through a range of motion.**

Group B (Sensor-Guided) will consist of **250** consecutive patients who will undergo primary unilateral PCL-retaining or – sacrificing TKA using the Stryker Triathlon Total Knee System *with* the use of VERASENSE to guide rotational alignment and balance. The sensor data will be used for balancing per the VERASENSE protocol below.

Each patient will be given a unique study number once informed consent has been obtained. The investigator will be blinded to the patient study number and the patient will be blinded to his/her assigned group. It will be important that all patients remain blinded to their assigned group. The patient will be informed during the consent process that they may or may not receive their knee replacement procedure using the VERASENSE Knee System.

Radiographic outcomes will be assessed on all patients within the first 12 weeks and at the annual visits. Any postop complications will also be monitored.

Surgical Protocol – Using VERASENSE

All knees will be prepared using standard instrumentation and a measured resection or gap balancing technique. The following steps will be performed when using VERASENSE:

Step 1: Establish Tibial Tray Rotation:

Select and position appropriate sized trial tibial tray. Align the tray to the anatomy (mid-medial third of the tubercle) as recommended by the manufacturer's surgical technique. Insert a single anterior or posterior pin (medially or laterally) into the trial tray to allow for internal / external rotational adjustment while maintaining optimal medial / lateral coverage.

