7.3 Patient Failure / Withdrawals

Removal or revision of any implant or malfunction of VERASENSE™ intra-operatively will be considered endpoints, with the patient being withdrawn from continued follow-up in the study. Every attempt must be made to ensure that all patients return for all of the post-operative assessments. However, patients are free to withdraw from the trial at any time and are under no obligation to provide a reason for doing so. All attempts should be made to ascertain whether a patient is lost to follow up, chosen not to return for follow-up or is deceased.

8. Medical Device Adverse Clinical Event Reporting

This study is not intended to prospectively assess the absolute product safety; however any device or procedure related safety issues will be documented as follows. The site will be required to transcribe onto the Safety Data CRF only those adverse clinical events that have been determined by the physician investigator to be attributable (even remotely) to 1) the knee arthroplasty procedure and/or 2) the use of the VERASENSE™ device.

The information to be captured on the CRF include the severity, relationship to knee arthroplasty procedure and the VERASENSE™ Device, outcome and treatment (when applicable).

a.

Expedited Reporting - Medical Device Reportable Events (21 CFR §803.3)

Expedited reporting to OrthoSensor is required for any fatal or serious injury (as defined below) that in the judgment of the physician investigator may have been attributed to the use of the VERASENSE™ device (only), or that the device was or may have been a factor in a death or serious injury, including events occurring as a result of: (1) failure; (2) malfunction; (3) improper or inadequate design; (4) manufacture; (5) labeling; or (6) user error.

The term “Serious injury” is defined per 21 CFR 803 as an injury or illness that:

1. Is life-threatening
2. Results in permanent impairment of a body function or permanent damage to a body structure;
3. Necessitates medical or surgical intervention to preclude permanent impairment of a body function or permanent damage to a body structure

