- Radiographic evaluation via Mediolateral and anteroposterior x-rays as is standard of care. The prevalence and location of radiolucency and/or osteolysis is evaluated on both AP and lateral views at each patient’s routine postoperative

follow-up visits. These evaluations are performed by each patient's operating surgeon.

- Complications, adverse events, and survivorship data will be collected and reported. This information will be gathered at each of the study follow-up visits.

c. Data Collection Periods:

Data will be collected pre-operatively, intra-operatively, and post-operatively at 6 weeks, 6 months, and 1 year. All time point windows are determined using the date of surgery (DOS) as day 0, including all annual visits. The visit windows are as follows:

Pre-operative: within 3 months prior to the date of the surgery excluding

*Pre-operative radiographs. Pre-operative radiographs taken within 12 months of scheduled knee replacement surgery are sufficient.

Intra-operative: within 2 weeks after the date of surgery

6 weeks: DOS + 6 weeks ± 4 weeks

6 months: DOS + 6 months ± 45 days

1 year: DOS + 1 year ± 90 days

2 year: DOS + 2 year ± 90 days

Table 1. Schedule of study assessments

Data Collected	Pre-op Baseline	Operative Discharge	6 Weeks	6 Months	1 Year	2 Years
Obtain Written Informed Consent	X					
Demographics	X					
Intra Operative		X				
EQ-5D	X		X	X	X	X
New-KSS	X		X	X	X	X
FJS			X	X	X	X
Knee Pain Evaluation Form				X	X	X
Radiographic Alignment	X		X	X	X	X
Adverse Event Reporting (When Present)		(X)	(X)	(X)	(X)	(X)

10. Analysis to be Performed on Data (e.g. Statistical Analysis)

Analysis of the data will be performed using SPSS version 21. Comparative Statistics will be run between outcomes data stratified by both groups: Analysis of variance (AVOVA) will be used to assess the difference between each group, with post-hoc t-tests to demonstrate significance. Separate analyses will be performed to evaluate power of sample sizes and any correlative affect that demographic/clinical variables may have on patient outcomes.

11. Monitoring of data collection

The Sponsor will monitor all data collected for accuracy and completion. The site will be monitored at least once per calendar year following the initial/first-monitoring visit.

12. Patient Identification

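### Section 8 enters an adverse event on the Safety Data CRF only if the investigator, who probably knows the arm, judges it attributable; counts of doubtful postoperative events could differ by arm through reporting alone

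*Combined protocol and SAP*

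**What the plan says.** Section 8 limits what sites transcribe to the Safety Data CRF to "only those adverse clinical events that have been determined by the physician investigator to be attributable (even remotely"). Either of two causes satisfies this test, and the section lists them as "1) the knee arthroplasty procedure and/or 2) the use of the VERASENSE™ device". The same section has the form record severity, the relationship to the procedure and to the device, outcome and treatment.

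Section 9b sets no attribution condition: "Complications, adverse events, and survivorship data will be collected and reported", with the information gathered at each follow-up visit. Section 5 likewise says that postoperative complications will be monitored.

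On blinding, Section 2 calls the study a "prospective, randomized (two-cohort) double-blinded clinical evaluation". Section 5 is narrower: "The investigator will be blinded to the patient study number and the patient will be blinded to his/her assigned group". In Group B, "The sensor data will be used for balancing per the VERASENSE protocol below". In Group A, "VERASENSE will be utilized in a surgeon-blinded fashion to record rotational alignment" and compartment pressures before closure. For follow-up radiographs, Section 9b states: "These evaluations are performed by each patient's operating surgeon".

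Section 10 plans comparisons of outcomes data between the two groups. It describes no separate safety analysis.

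**The concern.** An attribution test applied before entry decides which events the safety dataset contains. If the person applying it knows the arm, that knowledge can influence whether a borderline event is entered. The arms could then show different complication counts with the same underlying risk. An analysis of the Safety Data CRF alone could not detect this, because events judged unrelated would not be on it.

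What is at stake is any by-arm statement about complications. The plan says these will be reported, and its hypothesis favours the sensor-guided arm. There is also a consistency problem. A site working from Section 9b could record events that a site working from Section 8 would leave out.

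**Working it through.** **1. Who applies the test.** Section 8 names the physician investigator. No sentence says that this person knows the arm, so this is an inference. Section 5 blinds the investigator to the study number, not to the group. The operating surgeon acts on sensor readings in Group B and has them hidden in Group A, so their presence or absence reveals the arm. Section 9b gives the operating surgeon the follow-up radiographs, which suggests that the surgeon also sees the patient afterwards. The inference would fail only if attribution were made by someone else who is blinded to arm. The documents provide for no such person.

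**2. What passes the test or avoids it.**

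| Type of event | Route in the plan | Exposed to the gate? |
|---|---|---|
| Operative complications | Medical record (9b, operative data) | No |
| Implant removal or revision | Endpoint with no attribution test (7.3) | No |
| Range of motion, ligament stability | Knee Society Score at clinical visits (9b, Table 1) | No |
| Clear knee events, such as stiffness or instability | Safety Data CRF; related at least remotely to the procedure, in either arm | Little |
| Falls, medical readmissions | Safety Data CRF | Yes |
| Deaths | Safety Data CRF; also sought as a reason for non-return (7.3) | Partly |

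The gate therefore matters mainly for the last two rows.

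**3. Size, by illustration only.** The plan's one design figure is consistent: 250 + 250 = 500. It gives no event rate, capture share, alpha or power, so every input below except n = 250 per arm is an assumption. Call the arms X and Y, because the direction is unknown. Let both have true risk p and let a share c of events be recorded.

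- Recorded rate: r = p × c. Apparent risk ratio: c_Y / c_X, whatever p is.
- Chance of a significant result in the biased direction, two-sided alpha 0.05: Φ[(d − 1.96 × SE0) / SE1]. Here d = r_X − r_Y, SE0 = √[2 r̄(1 − r̄)/250] with r̄ the mean of the two rates, and SE1 = √[(r_X(1 − r_X) + r_Y(1 − r_Y))/250].

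Worked case: p = 10%, capture 90% versus 70%. Then r_X = 0.09, r_Y = 0.07, d = 0.02, SE0 = 0.02427 and SE1 = 0.02425. So (0.02 − 1.96 × 0.02427)/0.02425 = −1.14, and Φ(−1.14) is about 13%. With no bias it is 2.5%.

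| Capture X vs Y | Ratio | p = 5% | p = 10% | p = 20% |
|---|---|---|---|---|
| 95% vs 85% | 0.89 | 4.75% vs 4.25%; 4.5% | 9.5% vs 8.5%; 5.8% | 19% vs 17%; 8.4% |
| 90% vs 70% | 0.78 | 4.5% vs 3.5%; 8% | 9% vs 7%; 13% | 18% vs 14%; 23% |
| 90% vs 50% | 0.56 | 4.5% vs 2.5%; 23% | 9% vs 5%; 42% | 18% vs 10%; 73% |

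Each cell gives the recorded rates, then the chance of a significant result. At p = 10% the expected gaps are 250 × 0.01 = 2.5, 250 × 0.02 = 5 and 250 × 0.04 = 10 events. The normal approximation is rough at the lowest counts.

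**4. What those gaps require.** If clear events are always recorded and a share q of events is doubtful, overall capture cannot fall below 1 − q. Capture of 85%, 70% or 50% in arm Y therefore needs q of at least 15%, 30% or 50%. The lower rows of the table demand that many events be doubtful despite a low threshold. The documents do not say what share is.

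**The case against.** The strongest reply is that the gate is loose and not the only route. Even a remote link suffices, and the procedure limb applies equally to both arms. VERASENSE is inserted in both arms, so device attribution is not confined to Group B. Step 2 of the working lists the routes that avoid the gate. Section 8 also disclaims an aim of assessing absolute product safety, and the objectives in Section 3 do not include safety. Finally, Section 9b can be read as the general statement and Section 8 as the rule for carrying it out. Most of this stands, and it narrows the problem to doubtful postoperative events. It does not remove it: the plan still says complications and adverse events will be reported, and a disclaimer about absolute safety does not cover a comparison between arms.

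A reader might infer more than the documents support:

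- *That omitted events are lost for good.* Section 8 speaks of transcribing, which implies a source record, and Section 11 has the sponsor monitor data for accuracy and completion. Loss from the CRF is shown; permanent loss is not.
- *That stiffness or instability would go missing.* These readily count as remotely related to the procedure, and the Knee Society Score assesses range of motion and stability with no attribution step.
- *That releases and bone cuts are the main added exposure in Group B.* The plan does not say so, and nothing says that controls receive none.
- *That the bias favours the sensor arm, or has a known size.* No event rate, capture share or direction is given.

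**Conclusion.** The point holds in a limited form. Section 8 makes attribution a condition of entry to the Safety Data CRF, and Sections 5 and 9b set no such condition. By-arm counts of postoperative, non-revision events of doubtful relation could differ through reporting alone. This rests on the inference that the physician investigator is the operating surgeon, or otherwise knows the arm.

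The size is unknown. At an assumed true risk of 10%, the illustrations run from a gap of 1 percentage point (ratio 0.89) to 4 points (ratio 0.56), and the larger gaps need a large share of doubtful events. The documents do not establish that the complication comparison is biased, only that it is unprotected. The point does not affect the pain, function or alignment outcomes. It is worth acting on because the remedy is cheap.

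**What to change.** Change the Section 8 instruction so that every operated-leg complication, reoperation, readmission and death learned of at the scheduled visits is entered on the Safety Data CRF, whatever its attribution. Keep the existing fields for relationship to procedure and to device as descriptors, not as a condition of entry. State in Section 10 that any between-arm comparison of complications uses the unfiltered counts. Reconcile the wording of Section 8 with Section 9b so that all sites follow one rule.

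Note with the results that Section 7.3 withdraws patients from follow-up after removal or revision, or after an intraoperative VERASENSE malfunction. Their event capture is shorter, and the number withdrawn should be shown by arm.

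The cost is a revised instruction and some extra entries for events that are likely unrelated. Limiting the rule to events learned of at scheduled visits avoids a new search for every readmission over 2 years. One limit remains: the same investigator still asks about events and decides what counts as a complication, so the change removes the attribution gate but does not blind ascertainment.

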The clinical site must notify the OrthoSensor by email or telephone immediately but no later than 2 business days of any fatal or serious injury directly attributed to the use of the VERASENSE™ device. Notification to the IRB of record will be done according to the IRB’s specific procedures. OrthoSensor will be responsible for reporting the event to the FDA according to the timelines put forth in 21 CFR 803.

8.1 Risk Benefit Analysis:

As in any surgical procedure, certain risks are associated with total joint arthroplasty. These risks include but are not limited to: anaesthetic and post-anaesthetic reactions (such as hyperaemia), allergic reactions to prophylactic antibiotics or blood transfusions, damage to blood vessels or nerves or death. Post-operatively, a patient may experience thrombophlebitis, pulmonary embolus, dislocation, pain, limp, component loosening, osteolysis due to wear debris or the need for additional surgery. Fracture of the prosthesis is a potential complication.

As all patients recruited for this study are indicated for primary total knee arthroplasty with the device described in the protocol anyway, there is no known risk associated with participating in this study.

8.2 Protocol Departures:

Any departure from the current, approved protocol is considered to be a deviation or violation. Depending on severity of the departure, the reporting timeframe for the deviation/violation will change.

The following definitions apply:

- **Violation:** protocol deviation that is IRB/FDA reportable. For example, but not limited to, Informed Consent Documents not signed before surgery, a missing or lapsed IRB approval or an ineligible subject enrolled
- **Deviation:** protocol is not being followed exactly. For example, but not limited to, visits out of window, some data not collected for that visit or source documentation not available for a visit (CRFs used as source document).

8.3 Informed consent violation:

No patient will be enrolled in the study and have any study-related procedures performed, including completing subject clinical assessments, before an approved Informed Consent Document is signed. If this occurs, this is a VIOLATION and must be reported to OrthoSensor.

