It is the responsibility of the Principal Investigator to ensure that an Institutional Review Board (IRB) reviews the study and that the IRB acts in accordance with the requirements set forth in 21CFR56 – Institutional Review Boards. The Principal Investigator will forward copies of the protocol and all required documents to the IRB for review. Further, it is the Principal Investigator's responsibility to promptly inform the IRB of any revisions to the Clinical Study Protocol, to promptly report any serious medical device adverse events and/or unexpected events and to provide a periodic report of the study's progress to the IRB at intervals not to exceed 1 year. Any proposed amendment to the protocol that involves increased risk to the subject will require IRB approval prior to its enactment.

The investigator must forward written verification of the initial IRB review and approval to OrthoSensor before beginning the clinical study. The Principal Investigator must immediately forward copies of all subsequent correspondence between the Principal Investigator and the IRB concerning the continued approval of this clinical study, or withdrawal of such approval, to OrthoSensor.

16. Administrative Considerations

- **Ethics: The Declaration of Helsinki**

In any research on human subjects, each potential subject must be adequately informed of the aims, methods, anticipated benefits and potential hazards of the study and the discomfort it may entail. He or she should be informed that he or she is at liberty to abstain from participation in the study and that he or she is free to withdraw his or her consent to participation at any time. (21CFR312.120(3)I.9.

- **Changes to the protocol**

OrthoSensor and the Investigator must approve any changes made to this Protocol and/or any of the appendices and are subject to the approval of the relevant Institutional Review Board(s).

- **Clinical Investigator Agreement**

The Clinical Investigator Agreement is a written agreement to be signed by the Investigator that defines his/her responsibilities and willingness to follow the study protocol. This agreement must be signed by the Investigator and submitted to OrthoSensor before the initiation of the study.

- **Completion of the Study**

OrthoSensor will notify the Investigator when adequate data have been collected or when the clinical evaluation is terminated for any reason.

- **Reporting of Results**

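### Section 8a requires expedited notice of fatal or serious injuries with a possible device role, but words its 2-business-day limit only for injuries directly attributed to the device

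*Combined protocol and SAP*

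**What the plan says.** The safety rules are in Section 8 of the combined protocol and SAP, mainly in item a (Expedited Reporting).

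The trigger for expedited reporting has two parts, both confined to fatal or serious injury. The first covers an injury that in the investigator's judgment "may have been attributed to the use of the VERASENSE™ device (only"; the bracket closes after that word. The second covers cases where "the device was or may have been a factor in a death or serious injury". Six causes are then listed as included: failure, malfunction, design, manufacture, labeling and user error. A definition of serious injury follows.

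The deadline comes after that definition and before Section 8.1. The site must notify the sponsor immediately, and "no later than 2 business days of any fatal or serious injury directly attributed to the use of the VERASENSE™ device". The same paragraph sends IRB notice through each IRB's own procedures and closes with the sponsor's duty: "OrthoSensor will be responsible for reporting the event to the FDA according to the timelines put forth in 21 CFR 803".

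**The concern.** A section that defines a class of urgent events and then sets a time limit should use the same class both times. Here the class to be expedited rests on a possible or contributory role for the device, while the class given a number of days rests on direct attribution. A site that follows the deadline sentence as written could conclude that a serious injury with only a possible device role is outside the 2-business-day limit.

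The difference is not academic for this device. The sensor is a trial insert whose readings guide the surgeon. Section 5, Step 4 foresees soft-tissue release and sometimes further bone resection on the strength of those readings. Appendix II sets out releases and recuts by load, and Appendix I warns that assessing the knee in the wrong position could lead to too much release. Harm by that route passes through a surgical decision. An investigator could reasonably judge that the sensor may have been a factor without calling the injury directly attributable to it.

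What is at stake is timing. The sponsor reports to the FDA, and for an event at a site it depends on the site to tell it.

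**Working it through.** No arithmetic applies, and the plan gives no figure to reproduce. The check compares the two rules and then looks for any other rule that would close the gap.

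1. **Severity.** Trigger and deadline both concern fatal or serious injury. They agree.
2. **Causal threshold.** The trigger is met by possible attribution, or by an actual or possible contribution. The deadline is worded for direct attribution. In ordinary usage the second is narrower: every directly attributed injury meets the trigger, but an injury in which the device only may have played a part need not meet the deadline wording.
3. **The bracketed word in the trigger.** It could be taken to require that the device be the sole cause. It more naturally separates the device from the arthroplasty procedure, which the Safety Data CRF rule in Section 8 covers together with the device. The contributing-factor part would make little sense if sole cause were required. So the bracket does not bring the trigger down to the deadline's threshold.
4. **Listed causes.** The trigger names six, including user error. The deadline sentence names none and does not refer back to the list.
5. **Events left over.** Fatal or serious injuries that may be attributable to the device, or to which it may have contributed, but which are not judged directly attributed. These must be expedited and have no stated number of days.
6. **Other rules that might supply a limit.**
   - The Safety Data CRF (Section 8) takes events "attributable (even remotely) to 1) the knee arthroplasty procedure and/or 2) the use of the VERASENSE™ device". That threshold is lower still, but no deadline is given.
   - Section 9 has complications and adverse events gathered at each follow-up visit. That is a collection schedule, not a notice period.
   - IRB notice follows IRB procedures (Section 8a), and Section 15 obliges the investigator "to promptly report any serious medical device adverse events and/or unexpected events". The recipient is the IRB, and no number of days is stated.
   - The 21 CFR 803 timelines are stated for the sponsor's report to the FDA, not for the site's notice to the sponsor.

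None of these sets a site-to-sponsor limit in days for the events in step 5.

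**The case against.** The best defence is that the deadline is part of Section 8a. No heading separates it from the trigger, and the next heading is 8.1. The order is natural: what to expedite, what serious injury means, how fast to notify, and who tells the FDA. On that reading the 2-business-day sentence times every Section 8a report and is merely loosely worded. This may well be what the sponsor meant. It stands as an account of intent, but it does not change the words, and the multiple centers should not each have to infer it.

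A second defence is that the left-over events are neither unreported nor free of urgency. Their reporting to the sponsor is still mandatory and still labelled expedited. They also reach the CRF, the follow-up visits and the IRB. This stands in full. A reader might infer that possible device harms have no clock whatever or could go unreported, and the documents do not support that. What is missing is a number of days for notice to the sponsor.

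A third defence concerns weight. Section 4 describes the sensor as FDA-cleared and not investigational, and Section 8 says the study is not meant to assess absolute product safety. The mismatch affects neither allocation nor any planned comparison. That limits the importance of the point, but the protocol has chosen to set an expedited rule, and the rule should be consistent.

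**Conclusion.** The point holds as an internal inconsistency in Section 8a: the trigger is wider than the class of events to which the only site-to-sponsor limit in days is worded to apply. It should be corrected, because a site reading the sentence literally could delay notice of a serious injury with a possible or contributory device role.

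Its size cannot be stated. The documents give no event rates and nothing on how investigators would classify events. A reader might infer that most reportable events fall outside the limit, since harm from a guidance tool is seldom direct. The surgical sections show that such a route to harm exists, not how often it leads to serious injury. Nor does the point extend to every device event. Section 8a expedites only fatal or serious injury, and malfunction and user error appear there as causes of such injury, not as triggers of their own.

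The conclusion rests on two assumptions: that direct attribution carries its ordinary, narrower meaning, and that no site instruction outside these documents already applies the 2-business-day limit to all Section 8a events.

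**What to change.** In the 2-business-day sentence, replace the direct-attribution wording with a cross-reference, so that the limit applies to *any fatal or serious injury requiring expedited reporting under Section 8a*. A cross-reference is safer than restating the trigger, because a restatement could drop one of its two parts or some of the six causes and create a new mismatch. The change uses the protocol's own trigger and its existing deadline.

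If the sponsor did intend two tiers, Section 8a should say so and give the second tier its own stated limit.

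The cost is one amended sentence, notification of the sites and possibly a few more early notices to the sponsor. If the limit was always meant to cover all of Section 8a, only the wording changes.
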